2. Admission to the **Intensive Care Unit (ICU) for more than 48 hours**.
3. Availability of **chest CT imaging data**.

Exclusion Criteria

1. Patients aged <18 years.
2. Patients with incomplete medical records.
3. Absence of chest CT imaging or presence of technically inadequate/uninterpretable chest CT images.

Sample Size and Data Partitioning

This study is designed as a multicenter, large-sample, retrospective observational study and plans to include a total of 400 patients with ARDS who meet the eligibility criteria. Of these, 300 cases will be contributed by the primary institution and Sub-center 1, and 100 cases by Sub-center 2.

The study does not involve conventional experimental or control groups. Instead, cases will be partitioned into three datasets according to the model development workflow:

Training set: 276 cases (approximately 80% of the combined cases from the primary institution and Sub-center 2), obtained through stratified random sampling to preserve the distribution of mild, moderate, and severe ARDS;

Internal validation set: 69 cases (approximately 20% of cases from the same two centers), used to monitor overfitting and optimize model hyperparameters;

External test set: 55 cases, all derived from Sub-center 1 and entirely independent of the model development process, used to evaluate model generalizability.

Primary Outcome Measures

The primary outcomes of this study focus on the overall effectiveness of the proposed AI-based framework across three key clinical tasks:

(1) Accuracy of ARDS severity classification, defined as the agreement between model-predicted ARDS severity (mild, moderate, or severe) and the reference clinical classification based on the 2023 global ARDS criteria, assessed using chest CT images obtained within 24 hours of ICU admission;

(2) Treatment plan matching rate, defined as concordance between model-recommended and actual clinical management across five intervention modalities (mechanical ventilation, high-flow oxygen therapy, non-invasive ventilation, prone positioning, and neuromuscular blockade), evaluated at the time of index chest CT acquisition;

(3) Accuracy of 28-day in-hospital mortality prediction, defined as the ability of the model to predict all-cause in-hospital mortality within 28 days of ICU admission.

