These three outcomes collectively reflect the overall effectiveness of the model within a closed-loop framework encompassing disease stratification, treatment recommendation, and prognosis prediction.

Secondary Outcome Measures

Secondary outcomes include comparative performance improvement of the proposed model over commonly used baseline AI models; calibration performance of mortality prediction; interpretability analyses based on imaging-derived and clinical feature contributions; and assessment of the association between treatment concordance and 28-day in-hospital mortality using multivariable regression models.

Research procedures

1. Data collection

(1) Demographic and Baseline Clinical Data

Age, sex, body mass index (BMI), comorbidities (including chronic kidney disease, coronary artery disease, hypertension, diabetes, liver cirrhosis, HIV infection, etc.), primary etiology of ARDS, and receipt of mechanical ventilation, high-flow nasal oxygen therapy, or ECMO. BMI is calculated as weight (kg) divided by height squared (m^2).

(2) Physiologic Parameters

Body temperature (T), heart rate (HR), respiratory rate (RR), peripheral oxygen saturation (SpO_2), and mean arterial pressure (MAP).

(3) Laboratory Parameters

pH, partial pressure of arterial oxygen (PaO_2), fraction of inspired oxygen (FiO_2), partial pressure of arterial carbon dioxide (PCO_2), lactate (Lac), platelet count (PLT), white blood cell count (WBC), hemoglobin (Hb), serum creatinine, C-reactive protein (CRP), procalcitonin (PCT), international normalized ratio (INR), B-type natriuretic peptide (BNP), and interleukin-6 (IL-6).

(4) Ventilator or High-Flow Oxygen Parameters

Positive end-expiratory pressure (PEEP), tidal volume (TV), plateau pressure (Pplat), and flow rate (FLOW).

(5) Other Clinical Scores

Sequential Organ Failure Assessment (SOFA) score and Acute Physiology and Chronic Health Evaluation II (APACHE II) score.

2. CT Equipment and Scanning Parameters

Chest CT images included in this study were acquired from two CT scanners with the following parameters:

CT1 (64-slice): Manufacturer: Philips; Model: Brilliance; Tube voltage: 120 kV; Tube current: 1000 mA; Slice thickness: 5 mm; Slice interval: 5 mm; Pitch: 0.789:1.

CT2 (128-slice): Manufacturer: United Imaging; Model: uCTR760; Tube voltage: 120 kV; Tube current: 1000 mA; Slice thickness: 5 mm; Slice interval: 5 mm; Pitch: 0.984:1.

3. Quantitative Assessment of ARDS

Preliminary Image Processing

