The sample size was preliminarily estimated using the event-per-variable principle. The mortality prediction component is designed to include no more than 15 candidate predictors in the final multivariable logistic regression model. Following the commonly accepted criterion of at least 10 outcome events per predictor, a minimum of 150 death

events is required to ensure model stability and interpretability. Based on historical data from the participating centers, the in-ICU mortality rate among patients with ARDS is approximately 37.5%. Accordingly, the total target sample size for this study is estimated to be approximately 400 patients.

Statistical Analysis Plan

All eligible cases will be stratified and randomly sampled at an 8:2 ratio within Shanghai General Hospital and its affiliated centers to form the model training set and internal validation set. Cases from an additional participating center will be reserved as an independent external test cohort.

Model performance will be evaluated for three predefined tasks: ARDS severity classification, treatment strategy prediction, and mortality risk prediction. Performance metrics will include accuracy, balanced accuracy, area under the receiver operating characteristic curve (AUC), precision–recall curve analysis, and the Brier score. During model development, five independent repeated experiments will be conducted, and performance will be reported as mean values with standard deviations.

For comparative performance assessment, results from the five independent experiments will be compared using two-sided Wilcoxon rank-sum tests, with a significance threshold of 0.05. Different levels of statistical significance will be denoted using conventional symbols (e.g., “*”, “**”) corresponding to predefined P-value ranges.

To assess the association between model outputs and clinical outcomes, model-recommended intervention sets will first be encoded for agreement with actual clinical management. These agreement variables will then be incorporated into multivariable logistic regression models together with six imaging-derived anatomical features (e.g., diaphragmatic height, lung volume). Adjusted odds ratios with 95% confidence intervals will be reported, and a two-sided P value <0.05 will be considered statistically significant.

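### The concordance–mortality regression enters agreement without terms for treatment given or recommended, so its odds ratio can fall either side of 1 with the model's recommendation threshold alone

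*Combined protocol and SAP*

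**What the plan says.** Under Primary Outcome Measures, the treatment plan matching rate is "defined as concordance between model-recommended and actual clinical management across five intervention modalities". Under Secondary Outcome Measures, the plan lists "assessment of the association between treatment concordance and 28-day in-hospital mortality using multivariable regression models".

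The Statistical Analysis Plan gives the method: "model-recommended intervention sets will first be encoded for agreement with actual clinical management". It continues: "These agreement variables will then be incorporated into multivariable logistic regression models together with six imaging-derived anatomical features". Adjusted odds ratios with 95% intervals are reported, and "a two-sided P value <0.05 will be considered statistically significant".

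The documents do not state:

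- how agreement is coded (per modality or for the whole set, symmetric or directional);
- what threshold turns model output into a recommendation;
- which dataset the regression uses.

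No term for treatment given, treatment recommended, SOFA, APACHE II or ARDS severity is named for this regression. Both scores are collected, according to Research procedures, Data collection. Severity class and treatment information are added only in the separate mortality prediction work described later in the Statistical Analysis Plan.

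**The concern.** A symmetric agreement variable gives one value to two kinds of match (recommended and given; neither) and the other value to two opposite mismatches (recommended but not given; given but not recommended). Treated patients may differ in mortality from untreated patients because they are sicker or because treatment acts on death. If so, mortality among the mismatches depends on how many of them were treated. The model's threshold largely sets that mix: a model that recommends often produces mismatches that are mostly untreated, and one that recommends seldom produces mismatches that are mostly treated.

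The odds ratio is to be tested at 0.05 and read as evidence on whether care that matches the model goes with survival. Its direction could instead reflect a tuning choice that the plan leaves open.

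**Working it through.** **1. The plan's own figure.** The sample size section allows at most 15 predictors with "at least 10 outcome events per predictor": 15 × 10 = 150 deaths, and 150 / 0.375 = 400 patients. This reproduces and is not disputed. The plan gives no figure for the concordance odds ratio, so the inputs in steps 3 and 4 are assumptions.

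**2. Algebra.** Let G = given and R = recommended, both 0/1, and A = 1 when they match. Then A = 1 − G − R + 2GR. Entering A alone forces the G and R coefficients into a fixed ratio to the product, so any association of G or R with death loads onto A. If G and R are also in the model, A and GR give the same fit, and the log odds ratio for GR is twice that for A.

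**3. Hand calculation.** Let p = share treated, m1 and m0 = mortality in treated and untreated patients, and se and sp = the model's sensitivity and specificity for treatment actually given. Assume that, given treatment received, the recommendation is unrelated to death, so concordance has no effect.

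- Concordant mortality = [p·se·m1 + (1−p)·sp·m0] / [p·se + (1−p)·sp]
- Discordant mortality = the same with 1−se and 1−sp

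Take p = 0.5, m1 = 0.50 and m0 = 0.25 (37.5% overall).

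- se 0.90, sp 0.70: concordant (0.225 + 0.0875)/0.80 = 39.1%; discordant (0.025 + 0.0375)/0.20 = 31.3%; OR 1.41.
- se 0.70, sp 0.90: concordant (0.175 + 0.1125)/0.80 = 35.9%; discordant (0.075 + 0.0125)/0.20 = 43.8%; OR 0.72.
- se = sp = 0.80: OR 1.00.

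All three models match care in 80% of patients. With a weaker treated/untreated association (42.5% v 33%, OR about 1.5), the first two become 1.14 and 0.88. For a modality used in 20% of patients (55% v 33.1%), se/sp 0.30/0.95 gives 0.53 and 0.80/0.70 gives 1.08.

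**4. Null simulation.** Assumptions:

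- latent severity is standard normal, with log odds of death rising by 1 per SD, and overall mortality is 37.5%;
- treatment and model score each correlate 0.7 with severity and are independent given severity;
- treatment, recommendation and concordance have no effect on death;
- there is one modality, and the six features jointly explain a share R² of severity;
- large-sample odds ratios use n = 400,000.

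Agreement odds ratio from the planned model with half the patients treated:

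| R² of features | 10% recommended | 90% recommended |
|---|---|---|
| 0.3 | about 0.64 | about 1.69 |
| 0.6 | 0.75 | 1.44 |
| 0.9 | 0.92 | 1.10 |

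At n = 400 (600 replicates) and R² 0.3, the planned model falsely finds concordance protective in 55% of trials at a 10% recommendation rate, and harmful in 67% at 90%. At R² 0.6 these are 24% and 32%.

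With given and recommended added at R² 0.3, the agreement odds ratio is 0.93 to 1.05. Across treated shares of 30% to 70% and R² of 0.3 to 0.6, it stays within 0.92 to 1.09. Rejection is 2% to 5%. Those rejection rates are approximate, because some fits did not converge when a mismatch cell held about 2% of patients.

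**5. The role of severity.** If severity is fully adjusted and treatment does not affect death, the agreement odds ratio from the planned coding is 0.98 to 1.02 at every threshold. If severity is fully adjusted but treatment itself has an odds ratio of 1.5 for death, it again runs from 0.74 to 1.40.

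**The case against.** The strongest reply is that this is residual confounding by severity rather than a coding defect. Step 5 supports that where treatment has no effect on death, because full severity adjustment then removes the distortion. A reader might infer that the problem survives any added covariate, but the documents and calculations do not support that. It persists only while receipt is associated with death given the covariates, through residual severity or a treatment effect. The planned covariates are six anatomical features, so that condition is plausible, but it is not shown.

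The coding is also inferred. Symmetric pooling is the natural meaning of agreement and concordance, but directional coding is not excluded. What is certain is that the coding is undefined and that no main effects are named.

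Three further stronger readings do not hold:

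- **An under-recommending model always looks protective.** With 70% treated, 30% recommended and R² 0.3, the null odds ratio is 1.09.
- **This is the only analysis linking recommendations to outcome.** The Statistical Analysis Plan also adds treatment strategy information to mortality prediction, without saying whether that means recommended or actual treatment.
- **Comparing given with not given within recommendation strata answers the question.** That contrast is confounded by indication. It is (0.50/0.50)/(0.25/0.75) = 3.0 in the example of step 3, and about 1.8 to 2.0 in the null simulation, although concordance has no effect in either.

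**Conclusion.** The concern holds in a conditional form. The regression names agreement variables and six anatomical features, but neither component of agreement. On the symmetric reading, and if receipt remains associated with death after adjustment, the odds ratio can fall below or rise above 1 according to the threshold, with no effect of concordance.

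The sizes (1.41 v 0.72; about 0.64 to 1.69) rest on assumed mortality, correlations and a single modality. They cover deliberately wide recommendation rates. Over 30% to 70% at R² 0.3, the range is 0.86 to 1.33 with half treated, and with 70% treated it is 1.09 to 1.56 and does not cross 1. The mechanism is general; the magnitude is not.

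This is a secondary, associational analysis, so the primary outcomes are untouched. It should still be corrected before the regression is run, because its direction may be an artefact.

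**What to change.** - Define the agreement coding for each modality, name the dataset, and fix the recommendation threshold before outcomes are examined.
- For each modality in turn, fit given, recommended and their product, with the six features, SOFA or APACHE II, and ARDS severity.
- Base any concordance statement on the product term, not on an agreement term alone.
- Tabulate deaths in the four given-by-recommended cells, and show the result across thresholds as a sensitivity analysis.
- Label any given-v-not-given contrast within recommendation strata as descriptive only.

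**Cost.** SAP wording and re-coding of data already collected. Intervals widen and some cells will be sparse. One modality at a time needs 3 + 6 + about 2 = 11 terms, or 110 deaths if the plan's 10-per-predictor rule is borrowed for this regression; with three-level severity as two indicators, it is 12 terms and 120 deaths. Both are within 150 if all 400 patients are used and 28-day in-hospital mortality is close to the quoted in-ICU rate. All five modalities together would need 15 + 6 = 21 terms before severity is added, so 210 deaths and 210 / 0.375 = 560 patients. In the 55-case external set, about 55 × 0.375 = 21 deaths would not support the model.

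One limit remains. Mechanical ventilation, high-flow oxygen and non-invasive ventilation are partly alternatives, so not given for one may mean that another was given. The report should say so.

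### The concordance–mortality regression has no defined analysis set and no rule that recommendations be out-of-sample; cross-fitting would let all 400 patients be used

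*Combined protocol and SAP*

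**What the plan says.** Secondary Outcome Measures includes "assessment of the association between treatment concordance and 28-day in-hospital mortality using multivariable regression models". The Statistical Analysis Plan gives the method: "model-recommended intervention sets will first be encoded for agreement with actual clinical management. These agreement variables will then be incorporated into multivariable logistic regression models". The other covariates are six anatomical measures taken from the images, and adjusted odds ratios are tested at a two-sided 0.05 level.

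Sample Size and Data Partitioning divides the 400 patients into three sets: "Training set: 276 cases (approximately 80% of the combined cases from the primary institution and Sub-center 2"), 69 for internal validation, which also serves to tune hyperparameters, and 55 external patients from Sub-center 1 kept out of model development. The 8:2 ratio in the Statistical Analysis Plan agrees with this. Preliminary Image Processing instead describes a 60/20/20 split.

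The only sizing argument, in Sample size estimation, is for the mortality prediction model: "no more than 15 candidate predictors in the final multivariable logistic regression model" and "at least 10 outcome events per predictor".

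The plan does not state which patients enter the concordance regression, how many agreement variables it has, what the treatment task is trained to reproduce, or whether recommendations must be out-of-sample.

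**The concern.** The treatment task is described as predicting treatment strategy and is scored by its match to actual management. In retrospective data this implies that its training label is the treatment each patient received. A model fitted to a patient's own treatment tends to recommend that treatment back. Agreement in training patients then partly records model fit and not concordance with an independent recommendation.

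The two direct choices of analysis set each have a cost. Held-out patients give clean agreement but few deaths. All 400 give enough deaths, but most rows carry in-sample agreement and there are few apparently discordant patients. Naming an analysis set therefore does not resolve the matter; the way the recommendations are produced has to change. At stake is a secondary outcome reported with an odds ratio and a P value, where a null result could reflect the construction of the agreement variable or lack of precision.

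**Working it through.** **The plan's own figures.** 15 predictors × 10 events ÷ 0.375 = 400, which reproduces the target. For the split, the primary institution and Sub-center 1 give 300, so the primary institution gives 300 − 55 = 245. Development is 245 + 100 = 345; 0.8 × 345 = 276 and 0.2 × 345 = 69; 276 + 69 + 55 = 400.

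**Inputs that are inferred or borrowed.**
- Terms: five modalities (Primary Outcome Measures) plus six features = 11. One composite agreement variable would give 1 + 6 = 7.
- Mortality: 37.5% is an in-ICU rate, used because no 28-day in-hospital rate is given.
- Ten events per predictor is the plan's rule for another model and serves here only as a benchmark.

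**Deaths per term** = n × 0.375 ÷ terms.

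| Analysis set | n | Deaths | 11 terms | 7 terms |
|---|---|---|---|---|
| External only | 55 | 20.6 | 1.9 | 2.9 |
| External + internal validation | 124 | 46.5 | 4.2 | 6.6 |
| 60/20/20 of 400: test only | 80 | 30 | 2.7 | 4.3 |
| 60/20/20 of 400: test + validation | 160 | 60 | 5.5 | 8.6 |
| All | 400 | 150 | 13.6 | 21.4 |

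The rows with 124 and 160 are upper bounds, since the validation patients are used for tuning or model selection. With mortality assumed at 30% to 45% and 11 terms, the range is 1.5 to 2.3 per term at n = 55 and 3.4 to 5.1 at n = 124. Using all 400, the in-sample share is 276/400 = 69%, or 240/400 = 60% under the other split.

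**Power, under stated assumptions.** Take one binary agreement variable, 30% true discordance, 37.5% overall mortality and an odds ratio of 2.0 for discordant against concordant. Solving for the group risks gives 49.1% and 32.5% (check: 0.3 × 0.491 + 0.7 × 0.325 = 0.375). With d and c marking the discordant and concordant groups, SE = √[1/(n_d p_d) + 1/(n_d(1−p_d)) + 1/(n_c p_c) + 1/(n_c(1−p_c))], and power = Φ(ln OR/SE − 1.96) plus a negligible opposite tail.

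- n = 55: SE 0.601, power 21%, 95% CI a factor of 3.2 either way.
- n = 124: SE 0.400, power 41%.
- n = 400, all out-of-sample: SE 0.223, power 88%, CI factor 1.55.

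For all 400 with in-sample agreement, suppose apparent discordance in the 276 training patients is 5%. The discordant group is 276 × 0.05 + 124 × 0.30 = 51. The 276 × 0.25 = 69 truly discordant training patients move to the concordant group, whose risk becomes (69 × 0.491 + 280 × 0.325)/349 = 35.8%. The expected odds ratio is 1.73, with SE 0.302 and power 44%. Varying the assumed apparent discordance:

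| Apparent training discordance | Expected OR | Power |
|---|---|---|
| 5% | 1.73 | 44% |
| 10% | 1.77 | 55% |
| 15% | 1.82 | 65% |
| 20% | 1.87 | 74% |
| 25% | 1.93 | 82% |

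Over 20% to 40% true discordance, out-of-sample power with 400 is 78% to 91%. In-sample power at 5% apparent discordance is 42% to 44%.

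**Full model.** A 1,000-run simulation of an 11-term logistic model (assumed odds ratio 0.6 for agreement, 70% agreement) gave a median ratio of upper to lower 95% limit of about 25 at n = 55, 6 at n = 124 and 2.5 at n = 400.

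**The case against.** Several objections have force.

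- The plan does not say that it will use in-sample agreement, and a reader should not infer that it does; the gap is silence.
- The training label is an inference, strongly implied but unwritten.
- Nothing requires ten events per predictor for this analysis, so a low count here does not show that the plan breaks its own rule.
- The number of terms could be 7, and the power figures use a single agreement variable. Held-out counts stay below 10 either way under both stated splits.
- The five repeated experiments might redraw the 8:2 split. About 345 × (1 − 0.8⁵) = 232 development patients would then be held out at least once, or 287 with the external 55. That is 287 × 0.375 ≈ 108 deaths: 9.8 per term with 11 terms and 15.4 with 7. The plan does not state a redraw, and about 113 development patients would still never be held out.
- The loss from in-sample agreement depends on the degree of overfitting, which the documents do not give and which the validation set is meant to monitor. With mild overfitting the loss is small.
- Attenuation towards 1 needs misclassification unrelated to death. If patients who remain discordant after fitting are atypical or sicker, the direction is not assured.

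It is tempting to conclude that this outcome cannot be answered at all, or that a null result would mean nothing. The documents do not support that: at 25% apparent training discordance the expected odds ratio is 1.93 and power 82%. What stands is the unspecified analysis set, the missing out-of-sample requirement, and the shortage of deaths if only the held-out part of a single split is used. That shortage needs no overfitting assumption.

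**Conclusion.** The point holds as a worthwhile improvement to a secondary analysis. Under either stated split, the held-out patients give at most 8.6 deaths per term, and 1.9 to 6.6 under 276/69/55. Using everyone puts in-sample agreement into 60% to 69% of rows. Under the stated assumptions, power is 21% to 41% with held-out patients and 44% to 82% with in-sample agreement in all 400, against 88% with out-of-sample agreement in all 400. The 88% treats out-of-sample agreement as free of error.

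These sizes rest on the implied training label, the inferred 7 to 11 terms, the in-ICU rate as a stand-in, and the assumed discordance and odds ratio.

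A reader might also infer that a held-out recommendation is blind to the patient's own treatment. That does not follow. Data collection includes receipt of ventilation and high-flow oxygen and ventilator settings, and the section on etiological and respiratory mechanics classification adds mechanics to the model. If these feed the treatment task, even held-out recommendations see the treatment.

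**What to change.** Amend the Statistical Analysis Plan as follows.

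1. Compute agreement only from out-of-sample recommendations. Divide the 345 development patients into five folds of 69, train on the other 276 (the planned training size), tune inside those training folds, and recommend for the fold left out. Use the locked model for the 55 external patients.
2. Fit the regression on all 400 with a term for centre, and report the external-only estimate as descriptive. Two centre indicators make 13 terms with separate modalities (150/13 = 11.5 deaths per term) or 9 with a composite (16.7). At an assumed 30% mortality the first falls to 120/13 = 9.2.
3. State the training label and the number of agreement variables.
4. List the inputs of the treatment task, excluding the treatments being recommended and settings that reveal them.
5. Reconcile the 276/69/55 and 60/20/20 splits, and say whether the five repeats redraw the split.

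The cost is SAP wording, five fold models and the tuning fits inside each fold, with no new patients or data. The downside is that recommendations come from several models and not one locked model. Cross-fitting does not remove confounding by indication, so the odds ratio should be reported as an association.

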Chest CT images for all enrolled cases were exported from the hospital Picture Archiving and Communication System (PACS) in DICOM format. To minimize inter-scanner variability, all non-contrast CT images underwent standardized preprocessing. Using Python (version 3.9.13) and the open-source SimpleITK library (version 2.2.1), all images were converted to NIFTI format. Subsequently, each image was normalized to arrays with a uniform mean and standard deviation to reduce distributional differences across scanners. Following preprocessing, the images were fed into the deep learning (DL) model.

For dataset partitioning, the “createDataPartition” function from the *caret* package was used to perform stratified random sampling, assigning 60% of the data to the training set, 20% to the validation set, and the remaining 20% to the test set. The training set was used to fit the machine learning model, the validation set to select the best-performing model, and the test set to evaluate the final model performance.

Construction of a Deep-Learning Lung Segmentation Model

This study focuses on chest CT images with the lung as the organ of interest; therefore, the lung will be defined as the region of interest (ROI) for the deep-learning (DL) model. We plan to develop a U-shaped Transformer-based model for lung segmentation, with target classes including lesion regions, the whole lung, individual lobes, and all bronchopulmonary segments.

The U-Net architecture is widely used for medical image segmentation and comprises an encoder, a decoder, and skip connections. The encoder extracts local image features through successive convolutional operations and employs down-sampling to progressively expand the network receptive field. Conversely, the decoder upsamples processed features back to the original image resolution to enable pixel-level semantic inference. Skip connections fuse features from corresponding encoder and decoder layers, ensuring comprehensive feature maps that preserve precise spatial information alongside high-level semantics, which is critical for accurate segmentation. A Transformer can serve as the backbone within the U-Net encoder/decoder blocks; by using global attention mechanisms, it captures long-range dependencies and, in principle, attains a global receptive field.

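### The regression of 28-day mortality on treatment concordance lists no age, clinical severity or centre covariate and no analysis set, so fitted as listed its adjusted odds ratio would carry any severity difference that the imaging features miss.

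*Combined protocol and SAP*

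**What the plan says.** Secondary Outcome Measures lists "assessment of the association between treatment concordance and 28-day in-hospital mortality using multivariable regression models" and gives no adjustment set. The only specification is in the Statistical Analysis Plan: "These agreement variables will then be incorporated into multivariable logistic regression models together with six imaging-derived anatomical features (e.g., diaphragmatic height, lung volume". Two of the six features are given as examples and four are not named. The result is an adjusted odds ratio with a 95% interval, tested two-sided at 0.05.

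Concordance covers five modalities and is "evaluated at the time of index chest CT acquisition" (Primary Outcome Measures, item 2). The plan speaks of agreement variables in the plural and does not give their number or coding.

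Data collection includes age, PaO2, FiO2 and "Sequential Organ Failure Assessment (SOFA) score and Acute Physiology and Chronic Health Evaluation II (APACHE II) score". Three hospitals contribute patients.

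The analysis set is not stated, and the partitions conflict. Sample Size and Data Partitioning gives 276 training cases, 69 validation cases "used to monitor overfitting and optimize model hyperparameters", and "External test set: 55 cases, all derived from Sub-center 1 and entirely independent of the model development process". Preliminary Image Processing describes "assigning 60% of the data to the training set, 20% to the validation set, and the remaining 20% to the test set", with "the validation set to select the best-performing model".

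**The concern.** The five modalities include mechanical ventilation, prone positioning and neuromuscular blockade. Their use plausibly depends on how sick the patient is, so agreement with the model may depend on it too. Severity also predicts death. Any part of that shared dependence not captured by the six imaging features stays in the concordance odds ratio. Because the model is intended to inform treatment, a significant adjusted odds ratio below 1 could be read as a benefit of following it, and one above 1 as a harm.

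The missing analysis set is a second gap. If the treatment output is trained on the management patients actually received, agreement in training cases partly measures how well the model fitted those same patients. Validation cases are also not untouched, since they serve for tuning or model selection.

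**Working it through.** **1. The plan's own figure.** Sample size estimation uses 15 predictors, 10 deaths per predictor and 37.5% in-ICU mortality: 15 × 10 = 150 deaths, and 150 / 0.375 = 400. This reproduces. It belongs to the mortality prediction component; no size or power is given for the concordance regression. Below, 37.5% is assumed to hold for 28-day in-hospital death as well.

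**2. Does other text supply the covariates?** Later in the Statistical Analysis Plan, severity class is added to the inputs of the mortality prediction model and judged on balanced accuracy and Brier score. LASSO is used to interpret risk factors. Neither step is stated to estimate the concordance odds ratio.

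**3. Hand check of the mechanism (all gradients assumed).** Let concordance have no effect, with concordant and discordant groups of equal size and 25% against 45% severe. Let severity carry an odds ratio for death of 3, and overall mortality be 37.5%. Mortality is then about 28.4% in non-severe and 54.4% in severe patients.
- Concordant: 0.75 × 0.284 + 0.25 × 0.544 = 0.349.
- Discordant: 0.55 × 0.284 + 0.45 × 0.544 = 0.401.
- Odds ratio: (0.349/0.651) / (0.401/0.599) = 0.80.

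This uses no imaging adjustment, so it is an upper bound on the bias under these inputs. Reversing the gradient gives 1.25; equal severity gives 1.00.

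**4. Simulation with the listed imaging adjustment.** Assumptions: n = 400, no true effect, one binary agreement variable, latent normal severity, and mortality 20/35/57.5% by severity tertile (mean 37.5%). Six imaging features have the stated joint correlation with severity. The clinical set is a score and PaO2/FiO2 with the stated joint correlation, plus age and two centre terms as noise. Cells give median odds ratio / false-positive rate from 3,000 replicates.

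| Concordance by tertile | Imaging correlation | As listed | + clinical, corr. 0.5 | + clinical, corr. 0.7 |
|---|---|---|---|---|
| 85/75/60% | 0.5 | 0.75 / 22% | 0.78 / 18% | 0.82 / 14% |
| 85/75/60% | 0.7 | 0.80 / 17% | 0.83 / 13% | 0.84 / 12% |
| 60/75/85% | 0.5 | 1.33 / 21% | 1.29 / 17% | 1.23 / 13% |
| 60/75/85% | 0.7 | 1.26 / 15% | 1.23 / 12% | 1.20 / 10% |

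Allowing for variation between repeated runs, the ranges are 0.75–0.80 or 1.23–1.33 with 14–23% as listed, and 0.81–0.84 or 1.17–1.24 with 10–14% with clinical covariates at 0.7.
- Weak gradients (80/75/70% and the reverse), as listed: 0.89–0.91 or 1.11–1.13, with 7–8%.
- No gradient: about 1.00, with 5–6%.
- Imaging correlation 0.85, gradient 85/75/60%: about 0.85 with 10–11%, almost unchanged by clinical covariates.
- Standard error of the log odds ratio (85/75/60%, imaging 0.5): 0.238 as listed, 0.246 with clinical covariates at 0.7; 0.246 / 0.238 = 1.03.

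**5. Number of terms.** One agreement variable + 6 imaging + age + 1 score + PaO2/FiO2 + 2 centre = 12. Five agreement variables give 16.

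| Analysis set | Deaths at 37.5% | Per term, 12 | Per term, 16 |
|---|---|---|---|
| All 400 | 150 | 12.5 | 9.4 |
| Validation + external, 69 + 55 = 124 | 46.5 | 3.9 | 2.9 |
| Validation + test under 60/20/20, 80 + 80 = 160 | 60 | 5.0 | 3.75 |

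The 55 external cases alone give 55 × 0.375 = 20.6 deaths. They come from one centre, so the centre terms drop out: 20.6 / 10 = 2.1 per term. The 80 test cases under 60/20/20 give 30 deaths, 30 / 12 = 2.5 per term.

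**6. Multiplicity.** With five independent agreement variables and no effect, the chance of at least one P < 0.05 is 1 − 0.95^5 = 0.23.

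**The case against.** The plan is silent; it does not exclude. It says the agreement variables enter alongside six imaging features, not that nothing else does, and other covariates could be added at analysis. A reader might infer that severity will be left out, or that the odds ratio will be biased in the model's favour. The documents support neither: the list is not declared exhaustive, and they give no concordance gradient, so the bias could run either way or be absent.

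Imaging may also capture much of severity, since the protocol treats segmentation output as its main evidence for severity. If it does, clinical covariates add little, as the 0.85 case shows. Against that, the two features named are anatomical rather than measures of lesion burden, so a high correlation is not established either.

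The analysis is secondary and is already called an association, and on the illustrative figures adjustment reduces the bias without removing it. All of this stands. It limits the point to a specification gap and makes the wording of the conclusion as important as the covariates.

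The in-sample concern rests on the treatment output being trained on actual management. The outcome definition suggests this, but the documents do not say so. The conflict between the splits is a separate defect; it matters here because it prevents the analysis set from being inferred, and it adds nothing to the case for confounding.

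**Conclusion.** The point holds as a gap that should be closed before analysis. No text gives this odds ratio an age, clinical severity or centre covariate, or an analysis set, although the clinical variables are collected. Under moderately strong assumed gradients, the listed model would reject a true null in roughly 14–23% of studies instead of 5%. Suitable clinical covariates would bring that to 10–14% if they correlate 0.7 with severity, and to about 12–18% at 0.5. With weak gradients the excess is small, and with none it disappears. These figures show what could happen and do not estimate what will. They rest on assumed gradients and correlations, one binary agreement variable, and the in-ICU mortality rate standing in for 28-day in-hospital mortality.

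The number of agreement variables also matters: five of them, with the added covariates, fall just below the plan's own 10 deaths per term even with all 400 patients.

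**What to change.** 1. Add age, one severity score (SOFA or APACHE II), PaO2/FiO2 and centre to the six imaging features. Use the values closest to and not after the index CT, and state how patients without such values are handled.
2. Make one prespecified overall agreement variable the main exposure, define its coding, and treat modality-level results as exploratory.
3. Reconcile the splits in Sample Size and Data Partitioning and Preliminary Image Processing, then name the analysis set. Do not count in-sample agreement from training cases. Either use held-out cases only or, as an option, cross-fitted predictions for development cases together with the external cases. Say which of the five repeated experiments supplies the recommendation.
4. Report the result as an association in which residual confounding by severity remains possible.

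The cost is SAP wording and a check of time stamps on data already collected. The standard error rises about 2–4% in the 400-patient illustration. Some pre-CT values will probably be missing, and in patients already under treatment they may reflect that treatment. Held-out cases alone leave few deaths per term: about 46 deaths, 3.9 per term, in validation plus external cases under the centre-based split. The validation cases in that set have still been used for tuning. The external cases alone avoid this but allow no centre term. Cross-fitting keeps all 400 patients at 12.5 deaths per term, but it means refitting the model several times, and the agreement it yields is not that of the final model.
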